16.1.3. PRIMARY ANALYSIS OF PRIMARY EFFICACY VARIABLE

The primary objective of this study is to test the hypothesis that there is a difference between ensifentrine in comparison with placebo.

The change from baseline FEV₁ to average FEV₁ AUC_{0-12h} will be compared between ensifentrine and placebo using ANCOVA with fixed effects for treatment, region, background medication strata and smoking strata and baseline FEV₁ as covariate. Missing data will be imputed using imputation described in Section 16.1.2 of the SAP. The estimated treatment difference will be presented with 95% CI and associated p-value. Furthermore, SD will be presented for the treatment difference to check the sample size with 90% power. Summary statistics will be performed on the imputed values.

Model assumptions will be tested as per the following rules on the blinded data, before the DBL.

1. Residual vs Predicted plots will be created to check residuals are uncorrelated and normally distributed.
2. Normality of the data will be checked using Kolmogorov-Smirnov normality test.

If any of the checks specified above fail the test, then alternative approaches will be discussed, including different ways of transposing data. The SAP will be updated to reflect any changes prior to DBL.

Only spirometry measurements with best test review (BTR) grades “Acceptable” and “Borderline Acceptable” are used in the analysis and baseline calculations.

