6. Chest X-Ray should be obtained at Screening unless a CXR or a CT Scan obtained within the past 12 months are available. For subjects in Germany, if a CXR or CT scan is not available in the 12 months prior to Screening, the subject is not eligible for the study. (Section 8.1.7).
7. Screening spirometry: Pre-bronchodilator testing will be conducted prior to dosing with albuterol/salbutamol. Post-bronchodilator testing should be conducted between 15 and 30 minutes following administration of albuterol/salbutamol as per instructions in Sections 8.1.8 and 8.3.1.
8. Within 4 days prior to a scheduled in-clinic visit where spirometry is scheduled and blinded study medication will be administered, site staff will contact the patient (phone or text preferred), reminding them to take their blinded study medication and to record the date and start and stop times of the evening dose the night before the clinic visit in their paper diary. Patients will be reminded that prior to the clinic visit, they should withhold their nebulized study medication the morning of the visit as this will be dosed in the clinic, withhold rescue medication (albuterol/salbutamol) at least 4 hours prior to their visit and withhold their LAMA or LABA medication, and ICS (if applicable) until the end of the clinic visit. Request patients withhold caffeine and smoking as per Section 8.3.1.2. In addition, patients will also be reminded to bring their paper diary and remaining unused blinded study medication to the clinic visit to the attention of the unblinded site staff member. If a foil pouch is opened but the blinded study medication is not opened/not used, the patient should be instructed to seal the opened foil pouch (eg. tape) before returning it to the clinic (See Section 6 for details).
9. See Section 8.3.1.1 for details on Spirometry Training.
10. See Section 1.4, Schedule of Spirometry and In-Clinic Dosing with Blinded Study Medication. See Section 8.3.1 for instructions on spirometry. See Section 7.3.1.1 for spirometry procedures at Early Term/Withdrawal.
11. Health Outcomes: After completion of the mMRC at Randomization/Visit 1, the Health Outcome questionnaires and indexes should be completed in the order presented (Section 8.3.3)

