4.0 STUDY DESIGN

4.1 Overall Design

RPL554-CO-301 is a multicenter, randomized, double blind, parallel group, placebo controlled study to determine the efficacy and safety of ensifentrine 3 mg twice daily (BID) for 24 weeks with a subset of patients for 48 weeks, administered via nebulizer vs. placebo in patients 40 to 80 years of age with moderate to severe COPD (FEV₁ 30% – 70% of predicted, FEV₁/ forced vital capacity [FVC] ratio <0.7, with documented COPD symptoms).

Approximately 50% of patients recruited will be using stable background maintenance as *either* long-acting muscarinic antagonist (LAMA) *or* long-acting β 2 agonist (LABA) maintenance therapy and all patients will be provided with rescue albuterol/salbutamol for use as needed during the study. Up to 20% of patients are allowed to take inhaled corticosteroids during the study under certain provisions (see Sections 6.7.2 and 6.7.3). Washout of patients on stable background maintenance LAMA or LABA monotherapy for the sole purpose of study eligibility is not recommended.

Randomization will be stratified by three different factors: treatment duration (48 or 24 weeks), stable background maintenance LAMA or LABA therapy use (yes or no), and cigarette smoking (current or former). The 48 weeks strata will be randomized active to placebo 3:1, and the 24 weeks strata will be randomized active to placebo 1:1. Patients in the background maintenance LAMA or LABA therapy stratum must withhold Twice-Daily maintenance LAMA or LABA (or LAMA/ICS or LABA/ICS) for 24 hours and Once-Daily maintenance LAMA or LABA (or LAMA/ICS or LABA/ICS) for 48 hours prior to initiation of any spirometry. All patients must withhold short acting bronchodilator (SABA) rescue medication for at least 4 hours prior to initiation of any spirometry. All sites will use standardized spirometry and ECG equipment provided by a central vendor and all spirometry and ECGs will be over-read by the blinded central vendor.

Patients will be screened for eligibility before entering a 28-day run-in period to ensure a stable background maintenance LAMA or LABA bronchodilator medication regimen and to collect baseline information on symptoms and rescue medication use. Permitted rescue and background medications and the condition of their use during the study are described in Section 6.7.2. Prohibited medications and the prohibited time intervals prior to Screening are described in Section 6.7.3.

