9.0 STATISTICAL CONSIDERATIONS

9.1 Statistical Hypotheses

The aim of this study is to show superiority of ensifentrine over placebo regarding selected efficacy measures. The null hypothesis to be tested for each endpoint will be that there is no difference between ensifentrine and placebo, against the alternative hypothesis that ensifentrine is better than placebo. All tests will be two-sided at a 5% significance level. Primary and key secondary endpoints used for claims will be tested in a sequential order to preserve the alpha level. Testing will stop once a not significant result is achieved. Test order will be FEV₁ AUC_{0-12h} at 12 weeks, peak FEV₁ at 12 weeks, weekly mean E-RS total symptom score at week 24, SGRQ total score at 24 weeks, morning trough FEV₁ at Week 12, FEV₁ AUC_{0-4h} at 12 weeks and proportion of SGRQ responders at Week 24.

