9.2 Sample Size Determination

Approximately 800 patients will be randomized. The standard deviation for the change in FEV₁ AUC_{0-12h} is estimated to be 250 mL. With a 2-sided test at a 5% significance level and 500 vs. 300 evaluable patients in the two groups, there will be an 90% power to detect a true difference of 59 mL between the treatments. If the withdrawal rate at 24 weeks exceeds 25% overall, additional patients may be randomized to the study to compensate for the loss of data.

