16.1.1.1. AUC_{0-T}

Spirometry (FEV₁) will be performed at Screening and the following time points during, each treatment:

- Day 1: ≤40 minutes pre-dose (2 measurements); 30 minutes, 1, 2 and 4 hours post-dose.
- Week 6 and Week 24: ≤40 minutes pre-dose; 30 minutes, 1, 2 and 4 hours post-dose.
- Week 12: ≤40 minutes pre-dose; 30 minutes, 1, 2, 4, 6, 8 and 12 hours post-dose.
- Early Termination and no Week 12 visit spirometry assessment: ≤40 minutes pre-dose; 30 minutes, 1, 2, 4, 6, 8 and 12 hours post-dose.
- Early Termination but with Week 12 visit spirometry assessment: ≤40 minutes pre-dose; 30 minutes, 1, 2 and 4 hours post-dose.
-

Baseline FEV₁ is the mean of the two measurements taken before study medication on the day of first dosing, i.e. ≤40 minutes pre-dose on Day 1.

The average effect will be calculated as the AUC divided by the length of the time interval of interest (for example, 12 hours for AUC_{0-12h} or 4 hours for AUC_{0-4h}). AUC will be calculated using the trapezoidal method, as follows:

$$AUC = \frac{1}{2} \sum_{i=1}^{n-1} (T_{i+1} - T_i)(C_{i+1} + C_i)$$

Where T_i is the ith time value, C_i is the ith effect value, n is the number of time values. The change from the baseline FEV₁ to average FEV₁ (AUC) will be summarized and analyzed. If two last data points are missing the AUC is set to missing, that is for AUC_{0-12h} we require at least up to 8 hours of assessments and for AUC_{0-4h} we require at least up to 2 hours of assessments. This would mean if we only have 8 hours of assessments, then we would calculate AUC_{0-8h}, however it would still be labelled as AUC_{0-12h}. If there is no pre-dose measurement

available for the calculation of the AUC, then the AUC will not be calculated. The pre-dose measurement used in the calculation of AUC is the latest value measured ≤ 40 minutes pre-dose. The pre-dose value will be used as time 0 when computing AUC_{0-T} .

For AUC_{6-12h} we require at least the 6-hour and 12-hour timepoint for analysis.

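### Optional gain in precision: the primary ANCOVA adjusts only for single-session Day 1 FEV1, although screening pre-bronchodilator FEV1 is already collected and could be a second covariate

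*SAP*

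**What the plan says.** SAP Section 16.1.3 analyses the change to average FEV1 AUC0-12h at Week 12 "using ANCOVA with fixed effects for treatment, region, background medication strata and smoking strata and baseline" FEV1 as the covariate. SAP Section 7.1 lists no other continuous covariate, and protocol Section 9.4.1 specifies the same model. Baseline FEV1 "is the mean of the two measurements taken before study medication on the day of first dosing", within 40 minutes pre-dose (SAP Section 16.1.1.1). The primary imputation model in SAP Section 16.1.2 has the same terms plus the Week 12 value.

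An FEV1 from another day also exists. At Screening, "Pre-bronchodilator testing will be conducted prior to dosing with albuterol/salbutamol" (protocol Section 1.3, footnote 7), and Inclusion 7a needs the pre-bronchodilator ratio. Screening spirometry follows protocol Section 8.3.1, on central-vendor equipment with central over-read. The withholding rules for long-acting bronchodilators are those of later visits, and "All patients must withhold short acting bronchodilator (SABA) rescue medication for at least 4 hours prior to initiation of any spirometry" (protocol Section 4.1). The SAP uses the screening value for reversibility status and baseline tables (Sections 10 and 10.1). Neither document says why it is not a covariate.

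**The concern.** Two readings from the same 40 minutes average out test-to-test noise but share the patient's state on that day. That day-to-day component passes into the residual variance of the Week 12 comparison. A reading from a different day, under largely the same conditions, carries separate information on the patient's usual level, and a pre-randomization covariate in a linear model does not alter the mean-difference estimand.

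What is at stake is precision on the primary endpoint and on three FEV1 endpoints in the testing order (peak, morning trough, AUC0-4h). There is some reason to want it. The power statement takes all 800 planned patients as evaluable, some sites are removed from the mITT population, and the primary imputation uses nothing beyond the ANCOVA terms, so it recovers essentially no information for missing outcomes.

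**Working it through.** **Inputs from the documents.** "All tests will be two-sided at a 5% significance level" (protocol Section 9.1). From protocol Section 9.2: the SD of the change in FEV1 AUC0-12h "is estimated to be 250 mL", without saying whether this is before or after covariate adjustment; "500 vs. 300 evaluable patients in the two groups"; and "there will be an 90% power to detect a true difference of 59 mL between the treatments". The documents give no between-visit correlation and no day-to-day SD, so every such value below is an assumption.

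**1. The plan's own figure.** SE = 250 × √(1/500 + 1/300) = 18.26 mL. 59/18.26 − 1.960 = 1.272, so power is 89.8%. The difference detectable with 90% power is (1.960 + 1.282) × 18.26 = 59.2 mL. The stated figure reproduces.

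**2. Effect of a second covariate.** Let r² be the squared partial correlation of screening FEV1 with the outcome, given Day 1 FEV1 and the factors. Residual variance is multiplied by 1 − r². Taking 250 mL as the residual SD with one covariate:

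| r² | Residual SD (mL) | Detectable at 90% power (mL) | Power at 59 mL |
|---|---|---|---|
| 0 | 250.0 | 59.2 | 89.8% |
| 0.02 | 247.5 | 58.6 | 90.4% |
| 0.05 | 243.7 | 57.7 | 91.2% |
| 0.10 | 237.2 | 56.1 | 92.6% |
| 0.15 | 230.5 | 54.6 | 93.9% |
| 0.20 | 223.6 | 52.9 | 95.1% |

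**3. What r² might be.**

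- *Equal correlation ρ between all visits.* The variance ratio is (1 + 2ρ)/(1 + ρ)², a fall of 17%, 20% and 22% at ρ = 0.7, 0.8 and 0.9. This assumes no decay between 4 and 16 weeks, so it is the favourable end.
- *Unequal correlations.* r² = (r_SY − r_BY·r_SB)² / [(1 − r_BY²)(1 − r_SB²)], with S Screening, B Day 1 and Y Week 12. With r_BY = r_SB = 0.88 and r_SY = 0.85 to 0.86, r² is 11-14%. That gives a 28-day gap and an 84-day gap the same correlation. Raising r_SB to 0.92 gives 5-7%. Under pure first-order autoregressive decay r_SY = r_BY·r_SB, and the gain is 0.
- *Variance components.* Let the true-level SD be s, the day-to-day SD be d at both Screening and Day 1, and the unadjusted SD of change be 250 mL. With one covariate the residual variance is (62,500 − d²) + s²d²/(s² + d²). With two, d² in the second term becomes d²/2. For s = 500 and d = 100: 52,500 + 9,615 = 62,115 against 52,500 + 4,902 = 57,402, a fall of 7.6%; power goes from 90.0% to 92.1%. Over s = 400 to 600, the fall is about 2% at d = 50, 7-8% at 100, 15-17% at 150 and 21-23% at 177. The last is a ceiling, since 2 × 177² is about 250².

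**4. Simulation (4,000 trials per scenario, s = 500).** Type I error was 4.5-5.1% with one or two covariates. With d = 100, the mean SE fell from 18.2 to 17.5 mL and power rose from 90.1% to 92.1%. With an added screening-only shift of SD 150 mL, the SE fell only to 17.9 mL and power rose from 88.8% to 90.2%.

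**5. Downside and context.** The planned model has 7 parameters (intercept, treatment, two for region, background, smoking, baseline), leaving 793 degrees of freedom from 800. If r² = 0, the SE grows by √(793/792) = 1.0006, or 0.06%. If patients without a usable screening value were dropped, losing a fraction m would cancel a gain of r² = m; 2% lost cancels r² = 0.02. As an illustration, if 10% of evaluable patients are lost in proportion across arms, power is 86.6%, and a 7.5% variance reduction restores 89.0%. With 20% lost it is 82.4%, and a 15% reduction restores 88.0%.

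**The case against.** The strongest reply is that nothing here is wrong. Baseline is clearly defined, the covariate is prespecified in both documents, and the stated power reproduces. That stands in full; a reader might infer that the planned primary analysis is deficient, and the documents do not support that.

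A reader might also infer that power would rise from 90% to 94-96%. That needs equal correlations over 4 and 16 weeks, which no document supports. It also needs 250 mL to be the ANCOVA residual SD, which protocol Section 9.2 does not say. If 250 mL is unadjusted, then under that same equal-correlation model Day 1 adjustment alone multiplies the variance by (1 + ρ)/2, and power is already 94%, 93% and 91% at ρ = 0.7, 0.8 and 0.9.

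Nor is the washout identical in every respect. Protocol Table 8 allows some agents up to between 6 hours (ipratropium) and 1 week (oral beta2-agonists, and nebulized LAMA or LABA in the LAMA/LABA stratum) before Screening. Patients are also selected on screening spirometry, which can weaken its correlation with later values. Both shrink the gain; neither biases a randomized comparison.

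The practical need may be small. Protocol Section 2.2 reports 87 mL on 12-hour average FEV1 for 3 mg added to tiotropium; at an SE of 18.3 mL, power for that effect is 99.7%. Morning trough and AUC0-4h are tested only after E-RS and SGRQ, which FEV1 precision cannot help. The FEV1 secondary endpoints already use multi-visit imputation. These points limit the importance of the change, not its direction.

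Finally, it is not entirely free: it needs a rule for missing values, departs from protocol Section 9.4.1, and could put this study out of line with RPL554-CO-302 and the pooled analysis. That stands as a cost.

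**Conclusion.** The point holds as an optional efficiency improvement. The primary model leaves out a baseline measurement that is already collected and that could remove some of the day-to-day noise in the Day 1 value. The estimand and type I error are unaffected.

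The size is uncertain. Residual variance falls by 0% to about 20% across the assumed structures, slightly more at the ceiling of the components model. Roughly 2-15% is a reasonable working range, matching assumed day-to-day SDs of about 50 to 150 mL. That corresponds to power of about 90-94% if 250 mL is the one-covariate residual SD. The case for acting rests on asymmetry: if screening FEV1 adds nothing, about 0.06% of the SE is lost, provided that no patient is dropped.

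**What to change.** Before unblinding, add screening pre-bronchodilator FEV1 as a second continuous covariate in the ANCOVA and imputation models for FEV1 AUC0-12h, peak FEV1, morning trough FEV1 and FEV1 AUC0-4h. Keep change from the Day 1 baseline as the response.

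State a rule for screening values that are missing or fail the quality grades required by SAP Section 16.1.3: impute them without reference to treatment, so that no patient leaves the analysis. List the change in SAP Section 3.3 as a departure from protocol Section 9.4.1, and decide whether RPL554-CO-302 and the pooled plan should follow.

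The cost is SAP text, one model term and one degree of freedom. No new data are needed. SAP Section 16.1.3 already provides for blinded model checks and SAP updates before database lock, so the change could be made at that point.

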Patients will consent to either 24- or 48 weeks of treatment. Patients completing the run-in period and meeting all entry and Randomization Criteria will be randomized. The three different stratification factors will be applied at randomization. Details on blinded study medication and administration are provided in Section 6.0. The Study Schematic is shown in Section 1.2.

During the treatment period, patients will complete all assessments and procedures as outlined in the Schedule of Activities (Section 1.3) for either 24 or 48 weeks. Patients completing treatment will complete a Follow-Up within 4 to 10 days of the last scheduled study visit.

Patients meeting the withdrawal criteria during the study or who withdraw from the study for other reasons will be discontinued and requested to complete the Early Termination/Withdrawal Procedures and complete a Follow-Up within 4 to 10 days of the Early Termination/Withdrawal Visit.

Patients who permanently discontinue double blind study medication may remain in the study and follow the assessments and procedures as noted in Section 7.2.

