6.9. STRATA CALCULATIONS

There are three separate stratification factors used: treatment duration (48 or 24 weeks), background maintenance therapy strata and smoking strata. For all factors planned and actual will be created.

For treatment duration strata:

- Planned – As recorded in the Cenduit report.
- Actual – The actual treatment duration in which the patient consented to in the Patient Consent form
-
- In case when the randomized treatment duration stratum does not match with the treatment duration the patient consented to, the patient will be assigned to the stratum they consented to.

For background maintenance therapy strata:

- Planned – As recorded in the Cenduit report.
- Actual - As recorded in the “Concomitant medications” eCRF page: Patients that take LAMA or LABA (or LAMA/ICS or LABA/ICS) medication with start date being before or on randomization date and end date is either ongoing/post-randomization are classified as being on background maintenance therapy strata. Patients that do not meet this criteria will be classified as “No”.

For smoking strata:

- Planned – As recorded in the Cenduit report.
- Actual – As recorded in the “COPD and Smoking History” eCRF page.

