7. STATISTICAL CONSIDERATIONS

7.1. ADJUSTMENTS FOR COVARIATES AND FACTORS TO BE INCLUDED IN ANALYSES

The following covariates and factors are used in the analyses. For details of their inclusion in the models, see the specific analysis section.

Fixed effects: treatment (ensifentrine, placebo), region (Asia, Europe, North America), visit (Day 1, Week 6, Week 12, Week 18, Week 24), visit*treatment, stable background maintenance of LABA or LAMA (or LAMA/ICS or LABA/ICS) therapy use (yes, no), cigarette smoking (current, former)

Random effect: patient

Covariate: baseline

In case when the analysis model does not converge, the factor that causes it will be removed from the model.

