16.1.2. MISSING DATA METHODS FOR PRIMARY EFFICACY VARIABLE

The main analysis for the primary endpoint will include estimates from missing data imputation described below. This is done to investigate the influence of missing data due to drop-outs. Only patients with non-missing baseline will be included in the analysis.

The primary analysis will be analyzed using MI based on the missing data assumption Missing at Random (MAR). This process will follow four steps:

1. Partially impute the data for a monotone missing pattern with 100 as a number of imputations and “20905” as seed number. Employ the Markov Chain Monte Carlo (MCMC) method with treatment, region, background medication strata, smoking strata, baseline FEV_1 and average FEV_1 AUC_{0-12h} at Week 12.

1.1 The following SAS codes will be used:

```
proc mi data=<data1> out=<data2> nimpute=100 seed=20905;
  var <treatment> <region> <BackgroundMedStrata> <SmokingStrata>
  <baseline> <visits>;
  mcmc impute=monotone chain=multiple;
run;
```

2. Impute the monotone data using a regression imputation model. Apply by imputation using seed number “20905” with treatment, region, background medication strata, smoking strata, baseline FEV_1 and average FEV_1 AUC_{0-12h} at Week 12.

The following SAS codes will be used:

```
proc mi data=<data2> out=<dataout> nimpute=1 seed=20905;
  by imputation ;
  class <treatment> <region> <BackgroundMedStrata>
  <SmokingStrata>;
  var <treatment> <region> <BackgroundMedStrata> <SmokingStrata>
  <baseline> <visits>;
  monotone regression;
run;
```

3. Each multiple imputed dataset in Step 2 will be analyzed separately, as described in Section 16.1.3 of the SAP.
4. The estimates (LS means, SE, CI, and p-value) from the model analysis in Step 3 will be combined using Rubin’s combination rules for statistical inference.

Sensitivity analysis will be done using:

- Average imputation will be based on data collected on treatment at required visit, or at early termination visit. This will be done on patient level. If there is no such data available, impute with average change from baseline for the particular visit in the opposite randomized treatment group.

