16.2.4. SENSITIVITY ANALYSIS OF SECONDARY EFFICACY VARIABLES

For the key secondary endpoints the following sensitivity analysis will be performed at Week 12.

- Subgroup analysis as specified in Section 7.5 of the SAP.
- ANCOVA analysis with average imputation, as described in Section 16.1.2 of the SAP.
- ANCOVA analysis with MI, only considering baseline and Week 12 (for lung function parameters) in the imputation model, as described in Section 16.1.2 and 16.1.3 of the SAP.
- ANCOVA analysis with MI using the range data method as described in Section 16.2.2.3 for SGRQ total score and weekly mean total E-RS.
- Tipping point approach, as described in Section 16.1.2 of the SAP.
- Analysis with MI method, as described in Sections 16.2.2 and 16.2.3 of the SAP, based on PP population.
- For FEV₁ key secondary endpoints (FEV₁ AUC_{0-4h}, peak FEV₁, morning trough FEV₁) additional sensitivity analysis will be performed:
 - MMRM model with treatment, visit and treatment by visit as fixed effect; baseline as covariate; patient as random factor; unstructured covariance by visit. If the model does not converge a compound symmetry covariance structure will be used. Kenward-Roger method will be used to estimate the model degrees of freedom.
 -
- For weekly mean E-RS total score and SGRQ total score, additional analysis will be performed:
 - For weekly mean E-RS total score at 6, 12 and 24 weeks using ANCOVA approach, as described in Section **Error! Reference source not found.** of the SAP, all patients with baseline mean = 0 will be excluded.
 - For SGRQ total score at 6, 12 and 24 weeks, using ANCOVA approach, as described in Section 16.2.3.1 of the SAP, all patients with baseline assessment done after dosing time and date will be excluded.
 -

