16.3.3. ANALYSIS OF OTHER EFFICACY VARIABLES

Change from baseline to average FEV₁ AUC_{6-12h} will be analyzed using ANCOVA approach and missing data will be imputed using imputation, as described in Sections 16.1.3 and 16.2.2.1 of

[REDACTED]

the SAP, respectively.

Model assumptions will be tested and solved, if failed, as per Section 16.1.3 of the SAP.

The rate of and time to first moderate/severe COPD exacerbations will be analyzed in three cut-off rules:

- All patients (patients in 24-week and 48-week strata combined) using full study length
- Period truncated at Week 24 visit (patients in 24-week and 48-week strata combined)
- Patients in 48-week stratum using full study length

For each of the three rules above, the number of patients who experienced COPD exacerbation will be presented by week, follow-up and overall. Similarly, the duration of COPD exacerbation (in days) and the time in study will be calculated based on the cut-off rules.

Weekly percentage of patients who experienced COPD exacerbation will be based on the treatment population being analyzed. For All patients and Period truncated at Week 24 visit, the percentage will have denominator of mITT population. Analysis using 48-week stratum only will have mITT patients in this stratum as denominator.

For each cut-off rule, the number of moderate/severe COPD exacerbations will be analyzed using a negative binomial model adjusting for treatment, region, actual background medication strata and actual smoking strata, as well as using log study time (years) as an offset. If the model does not converge, the covariate that causes the issue will be removed from the model. The number of patients who experienced exacerbations and the number of exacerbations will also be presented using the data used to analyze negative binomial model.

The logic for time in study used as offset or for censoring purpose is as follows:

- For 24-week completers, use the day of final week 24 clinic visit. For 48-week completers, use the day of the final week 48 clinic visit.
- For non-completers who are not lost to follow-up, use the end of study date, which is assumed to be their end of study visit.
 - If no end of study date, use the last site contact out of any assessment (excluding eDiary)
- For subjects who are lost to follow-up, the censoring date will be at their last reported site contact.

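### Treatment duration is the only stratification factor that changes the allocation ratio, yet no pooled efficacy or imputation model includes it

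*SAP*

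**What the plan says.** Protocol 4.1 sets the allocation: "The 48 weeks strata will be randomized active to placebo 3:1, and the 24 weeks strata will be randomized active to placebo 1:1". The same section says how a patient reaches a stratum: "Patients will consent to either 24- or 48 weeks of treatment". The Protocol synopsis plans about 400 patients per stratum and 500 ensifentrine and 300 placebo patients overall.

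SAP 6.9 states: "There are three separate stratification factors used: treatment duration (48 or 24 weeks), background maintenance therapy strata and smoking strata". The models then use two of the three:

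- **Primary ANCOVA (SAP 16.1.3):** "ANCOVA with fixed effects for treatment, region, background medication strata and smoking strata", plus baseline FEV1. The secondary ANCOVAs (16.2.3.1) refer back to it.
- **General factor list (SAP 7.1):** it opens "Fixed effects: treatment (ensifentrine, placebo), region (Asia, Europe, North America), visit" and goes on to background therapy and smoking, but not duration.
- **Imputation (SAP 16.1.2, and likewise 16.2.2.1):** "Employ the Markov Chain Monte Carlo (MCMC) method with treatment, region, background medication strata, smoking strata", plus baseline and visit data.
- **Responder models (SAP 16.2.3.2, 16.3.3):** logistic regression with treatment, region, background therapy, smoking and baseline.
- **MMRM sensitivity analysis (SAP 16.2.4):** "MMRM model with treatment, visit and treatment by visit as fixed effect; baseline as covariate; patient as random factor", with none of the three stratification factors.
- **Exacerbations (SAP 16.3.3, 16.3.4):** "negative binomial model adjusting for treatment, region, actual background medication strata and actual smoking strata", with log-rank and Cox analyses stratified by region, background therapy and smoking.

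Protocol 9.4.1 has the same omission, and SAP 3.3 gives no reason for it. Duration is also absent from the subgroups in SAP 7.5 and the primary sensitivity analyses in SAP 16.1.4. Elsewhere the SAP uses it only to split, restrict or truncate data: disposition, compliance, laboratory, ECG, vital signs, and the exacerbation periods.

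**The concern.** If a stratification factor has the same allocation ratio at every level, leaving it out of the model mainly affects precision, because the arms are balanced on it by design. Duration is different. Its levels carry different ratios, so the arms are unbalanced on it by design, and a larger trial would not reduce the imbalance. Treatment is randomised only within duration stratum.

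The pooled contrast is therefore unbiased only if duration stratum is unrelated to outcome given baseline, region, background therapy and smoking. The plan neither states nor tests this. Patients who accept 48 weeks may differ from those who accept 24, and a region factor with three broad levels need not capture that.

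At stake is the confirmatory comparison. The primary endpoint opens the testing sequence for six key secondary endpoints (SAP 7.4), so a false positive there carries forward.

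**Working it through.** **1. The plan's own figure.** Protocol 9.2 gives SD 250 mL, 500 vs 300 evaluable patients, two-sided 5%, and 90% power at 59 mL.

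- SE = 250 × √(1/500 + 1/300) = 18.26 mL
- Power = Φ(59/18.26 − 1.96) = 89.8%

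The stated 90% reproduces, so this is not a sample-size error.

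**2. Built-in imbalance.** Planned counts (ensifentrine:placebo) are 200:200 in the 24-week stratum and 300:100 in the 48-week stratum.

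- Share in the 48-week stratum: 300/500 = 0.600 vs 100/300 = 0.333
- Difference = 0.267

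**3. Bias and error without the term.** Let D be the mean change in the 48-week stratum minus that in the 24-week stratum, after the planned covariates. D is an assumption; the documents do not give it, and it may have either sign. Take 250 mL as the residual SD.

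- Bias b = 0.267 × D
- Two-sided type I error = Φ(−1.96 + b/18.26) + Φ(−1.96 − b/18.26)
- Power at 59 mL when D is negative = Φ((59 − size of b)/18.26 − 1.96)

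| Size of D (mL) | Size of bias (mL) | Two-sided type I error | Power at 59 mL if D is negative |
|---|---|---|---|
| 0 | 0 | 5.0% | 89.8% |
| 10 | 2.7 | 5.2% | 87.0% |
| 25 | 6.7 | 6.5% | 81.8% |
| 50 | 13.3 | 11.3% | 70.6% |

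The two-sided error rises for either sign of D. The excess favours ensifentrine only when D is positive; when D is negative, a real effect is understated.

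**4. With the term.**

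- Information = 200 × 200/400 + 300 × 100/400 = 100 + 75 = 175, against 500 × 300/800 = 187.5 without it
- SE = 250/√175 = 18.90 mL, that is 18.90/18.26 = 1.035 times the unadjusted SE
- Power at 59 mL = Φ(59/18.90 − 1.96) = 87.7%

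**5. Simulation.** In 20,000 least-squares trials per scenario with the planned counts, type I error at D = 0, 25 and 50 mL was 5.1%, 6.7% and 11.1% without the term. With it, the error was 5.1%, 5.1% and 4.9%.

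**6. Pooled full-length exacerbation rate, assuming complete follow-up.**

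- Ensifentrine: 200 × 24 + 300 × 48 = 19,200 patient-weeks, of which 7,200 (37.5%) fall after Week 24
- Placebo: 200 × 24 + 100 × 48 = 9,600 patient-weeks, of which 2,400 (25.0%) fall after Week 24
- If the later rate is r times the earlier rate, a true rate ratio of 1 becomes (0.625 + 0.375r)/(0.75 + 0.25r)
- Assumed r = 0.8 gives 0.97; r = 1.25 gives 1.03

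This component is small. A rate difference between strata would add to it, and the log-time offset does not remove that.

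**The case against.** The strongest reply is that the harm depends entirely on D. Both strata share the same entry criteria and identical assessments over the first 24 weeks, and the primary endpoint is a change from baseline at Week 12. A D of 50 mL would be 50/59 = 85% of the targeted effect, with no support in the documents; at 10 mL the error is 5.2%. This limits D and stands as a caution on size, but it does not make D zero. For weekly E-RS and rescue use, measurement also differs somewhat by stratum. In patients who stay in the study, SAP 6.4 ties the Week 24 window to the actual Week 24 visit in the 24-week stratum, but counts it back 175 to 168 days from the Week 48 visit in the 48-week stratum.

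The power loss is also shown at the smallest targeted effect. Protocol 2.2 reports 87 mL for average FEV1 over 12 hours with 3 mg added to tiotropium. At that effect and D = −50 mL, power is Φ((87 − 13.3)/18.26 − 1.96), about 98%. That is fair, but it does not touch the type I error.

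The exacerbation endpoints lie outside the testing hierarchy. The Week 24 truncation removes the unequal later person-time, and the analyses limited to the 48-week stratum have a single ratio and are unaffected. So the concern is minor there. Adding duration to the log-rank and Cox strata would also double the cells from 3 × 2 × 2 = 12 to 24. The 100 placebo patients of the 48-week stratum would then average about 8 per cell.

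Finally, Protocol 9.4.1 itself names the models without duration, so the change is a departure from the protocol that must be recorded.

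**Conclusion.** The concern holds. Duration alone changes the allocation ratio, patients enter it by consent, and no pooled efficacy or imputation model contains it. The bias in the primary contrast is 0.267 × D. Over an assumed range of 0 to 50 mL for the size of D, that is 0 to 13.3 mL, with two-sided type I error from 5.0% to 11.3%. These figures rest on the planned counts, a residual SD of 250 mL and a D that the documents do not supply.

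The omission is certain; bias is possible but not shown, and its sign is unknown. The point bears most on the primary and key secondary ANCOVA, logistic and imputation models. It should be settled before unblinding, because a term added afterwards would be post hoc.

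**What to change.** - Add the planned (as-randomised) duration stratum as a fixed factor to the primary and secondary ANCOVAs, the logistic models and both steps of every multiple imputation model.
- Do the same in the MMRM and the pooled negative binomial model, and stratify the pooled log-rank and Cox analyses by it. For those two, state in advance which stratifier gives way if cells are too sparse.
- Use the planned value, because it set each patient's allocation probability. SAP 6.9 moves mismatched patients to the stratum they consented to, so the SAP must name the version used.
- List the factor in SAP 7.1 and record the departure from Protocol 9.4.1 in SAP 3.3. SAP 7.1 drops a factor that prevents convergence; say that duration is kept.
- Optionally add duration to the SAP 7.5 subgroups, so that any difference is visible.

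The planned stratum variable is already to be created under SAP 6.9, so the work is wording and one model term. If D is zero, the statistical cost is a 3.5% larger SE and about 2 points of power at 59 mL (89.8% to 87.7%). Restoring the unadjusted precision would take about 800 × 187.5/175 = 857 patients; otherwise the SAP should say that the lower power is accepted.
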